## Example: A severe hyperglycemia AE with the following event description would have the following causality assessment for device relatedness:

Improved glucose without an infusion set/site change	Not related
Changed infusion set with glucose improvement	Possible
Infusion set fell out, bent cannula, occlusion alarm	Causal relationship

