# CIP337 Clinical Investigation Plan Page 26 of 97 Medtronic D00459337 Version A Page 26 of 97 Medtronic

or other approved ketone meter if the Accu-Chek Guide Link study meter reading is greater than 300 mg/dL.

As a precaution, subjects and their parents/caregivers (if applicable) will be told that subjects should keep their own insulin pump supplies in a safe place and to have back up supplies on hand (such as insulin and syringe, or insulin pen) in the event they are asked to revert back to their own therapy during the study or experience study pump issues (i.e., infusion set occlusion with high glucose).

Subjects and their parents/caregivers (if applicable) will be instructed to insert the DS5 into subjects only in the locations that are specified in the User Guide. Reminders will be given to subjects and their parents/caregivers (if applicable) at each office visit. Information about sensor insertions will be collected at each study visit on an electronic case report form (eCRF) in the study database, e.g., insertion location.

Subjects and their parents/caregivers (if applicable) will be trained on all parts of the device system. This will involve live training conducted by the investigational center staff. A training checklist for both subject and parents/caregivers (if applicable) will be implemented and completed. Parents/caregivers (if applicable) should be available for relevant parts or all of this training, either in person or virtually.

After completion of training on the study devices, subjects and their parents/caregivers (if applicable) may attend additional visits in the days immediately following the start of system use, as needed.

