
 
the risk of malfunction of the components of the system (pump, software, infusion set and reservoir) as well as the risk of use error during use of the system. DDs or use errors can result in administration of too much or too little insulin which can lead to the following clinical consequences:
 
Hypoglycemia
 
Hyperglycemia
 
Diabetic ketoacidosis
 
Severe hypoglycemia with or without associated seizure, coma or death
 
Kinked cannula leading to hyperglycemia
 
Infusion set disconnection from pump leading to hyperglycemia
 
Subject removes the reservoir from the pump but forgets to disconnect the infusion set from the body which results in hypoglycemia or severe hypoglycemia
 
Dislodged cannula leading to hyperglycemia
 
A pump error may lead to under delivery or over- delivery of insulin
 
Battery failure – no insulin delivered
 
	
 
Follow the provided user guides & instructions for insulin and insulin pump management which includes information on infusion set change.
 
Train prior to study device use on appropriate device use and diabetes management principles and instruct to call investigator with problems.
 
Instruct to check their meter glucose if their high or low symptoms do not match their sensor alerts or SG readings in order to make diabetes treatment decisions.
 
Instruct to check their meter glucose if there are any concerns that the SG value is not accurate.
 
Instruct to change infusion set if suspected catheter occlusion or administer insulin with syringe for persistent hyperglycemia especially if ketones develop.
 
Parent(s)/guardian(s), if applicable, should be present at night with subjects and will be trained on study device and diabetes management principles and instructed to call investigator with problems.
 

CIP337 Clinical Investigation Plan		
D00459337 Version A	Page 60 of 97	Medtronic

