#### It is the responsibility of the investigator to follow their IRB reporting requirements.

#### **11.6 Causality Assessment**

An AE is not automatically related to the study device or procedure simply because the subject is wearing the device and participating in the study. The event should be reviewed to determine if the device or study procedure could have possibly caused the event and therefore is related to the study device or procedure.

Causality assessment is the determination of the relationship between an AE and the device being studied. It is expected that the investigational center will review all elements surrounding the AE to properly assess the causality of the event to the study device or to a study procedure.

This review would include the subjects' description of the event, study device uploads and medical records (if applicable) from the treating facility. These records will be made available to sponsor.

Investigators should classify the relationship between the AE and the study device or study procedures using one of the four possible causality categories listed below:

- **Not related:** relationship to the device, comparator, or procedures can be excluded when:
  - the event has no temporal relationship with the use of the investigational device or the procedures related to the application of the investigational device;
  - the event does not follow a known response pattern to the medical device (if the response pattern is previously known) and is biologically implausible;
  - the discontinuation of medical device application or the reduction of the level of activation/exposure – when clinically feasible – and reintroduction of its use (or increase of the level of activation/exposure), do not impact on the event;
  - the event involves a body-site or an organ not expected to be affected by the device or procedure;
  - the event can be attributed to another cause (e.g., an underlying or concurrent illness/ clinical condition, an effect of another device, drug, treatment or other risk factors);
  - the event does not depend on a false result given by the investigational device used for diagnosis, when applicable;

In order to establish the non-relatedness, not all the criteria listed above might be met at the same time, depending on the type of device/procedures and the event.

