## CIP337 Clinical Investigation Plan Page 70 of 97 Medtronic D00459337 Version A Page 70 of 97 Medtronic

another device, drug or treatment). Cases where relatedness cannot be assessed, or no information has been obtained should also be classified as possible.

- **Probable**: the relationship with the use of the investigational device, comparator, or the relationship with procedures, seems relevant and/or the event cannot reasonably be explained by another cause.
- **Causal relationship:** the event is associated with the investigational device, comparator, or with procedures beyond reasonable doubt when:
  - the event is a known side effect of the product category the device belongs to or of similar devices and procedures;
  - the event has a temporal relationship with investigational device use/application or procedures;
  - o the event involves a body-site or organ that
    - the investigational device or procedures are applied to;
    - the investigational device or procedures have an effect on;
  - the event follows a known response pattern to the medical device (if the response pattern is previously known);
  - the discontinuation of medical device application (or reduction of the level of activation/exposure) and reintroduction of its use (or increase of the level of activation/exposure), impact on the event (when clinically feasible);
  - other possible causes (e.g., an underlying or concurrent illness/clinical condition or/and an effect of another device, drug or treatment) have been adequately ruled out;
  - harm to the subject is due to error in use;
  - the event depends on a false result given by the investigational device used for diagnosis, when applicable;

In order to establish the relatedness, not all the criteria listed above might be met at the same time, depending on the type of device/procedures and the event.

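### The Section 11.6 causality example rates severe hyperglycemia that improves without a set change as not related, even when the insulin that worked bypassed the infusion set

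*Protocol*

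**What the plan says.** Protocol Section 11.6 ends with a three-row example, introduced as follows: "A severe hyperglycemia AE with the following event description would have the following causality assessment for device relatedness".

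- Row 1: "Improved glucose without an infusion set/site change" is rated *Not related*.
- Row 2: a changed set followed by better glucose is rated *Possible*.
- Row 3: "Infusion set fell out, bent cannula, occlusion alarm" is rated *Causal relationship*.

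No row mentions the route of the corrective insulin.

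The general text of 11.6 sets the tests that the example should illustrate. The investigator asks whether the device or procedure "could have possibly caused the event and therefore is related to the study device or procedure". *Not related* is for events where the "relationship to the device, comparator, or procedures can be excluded when" certain criteria apply. Under *Possible*, the text adds: "Cases where relatedness cannot be assessed, or no information has been obtained should also be classified as possible".

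Insulin outside the pump is foreseen. Table 4 (Section 10.1, risks with insulin administration and pumps) says: "Instruct to change infusion set if suspected catheter occlusion or administer insulin with syringe for persistent hyperglycemia especially if ketones develop". Section 5 has subjects keep a syringe or pen with insulin as back-up for pump problems, and names set occlusion with high glucose as one of them. The infusion set counts as a device here, because Section 11.2 extends the word to any device used in the study.

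**The concern.** Row 1 uses improvement without a set change as evidence that the set was not at fault. That inference is sound when the insulin that worked went through the set. It fails when the insulin was injected, because the recovery then says nothing about the set in either direction. Row 1 treats the two situations alike.

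At stake is the relatedness code of a severe hyperglycemia event and, through it, the rate of device related adverse events that the Data Monitoring Committee reviews under Section 12.2. For the case described, the error can run only toward understating relatedness.

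**Working it through.** The plan gives no figure on this point, so the check is mainly one of wording.

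**Step 1: which row fits.** Take a set that fails silently: no alarm, no bent cannula, not dislodged. The subject injects insulin, leaves the set in place, and glucose improves.

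- Row 3 needs a visible or alarmed failure, so it does not apply.
- Row 2 needs a set change, so it does not apply.
- Row 1 needs only improvement without a set change, so it applies as written and gives *Not related*.

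**Step 2: what the general text gives.** Set occlusion and site failure leading to hyperglycemia are listed risks in Table 4, so a set problem is a plausible cause. Improvement after an injection neither confirms nor excludes it. The exclusion test for *Not related* is therefore not met on this evidence, and an event whose relatedness cannot be assessed goes to *Possible*. The example and the general text disagree for this case.

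**Step 3: can the case arise under the protocol.** Yes. Table 4 joins the set change and the syringe with an *or*. Its separate entry on infusion sets advises replacing the set, but for hyperglycemia already attributed to occlusion. A silent failure has not been recognized as such.

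**Step 4: size per event.** Section 12.2 defines the monitored rates as events per 100 patient-years. One event moved out of the device related count lowers that rate by 100 / patient-years, where patient-years = subjects × days / 365.25. The inputs are 200 subjects entering the study period (Section 8.1), 90 days to Visit 15 (Section 9.1.1), and about 120 days of participation (Section 5.1).

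- 200 × 90 / 365.25 = 49.28 patient-years; 100 / 49.28 = 2.03
- 200 × 120 / 365.25 = 65.71 patient-years; 100 / 65.71 = 1.52
- One age group of 100, 90 days: 24.64 patient-years; 100 / 24.64 = 4.06
- One age group of 100, 120 days: 32.85 patient-years; 100 / 32.85 = 3.04

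These figures assume no dropout, an even split between age groups, and that *Possible* counts as device related, as the opening of 11.6 suggests. They would hold for any single miscoded event. They show the scale of one error and do not predict how many will occur.

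**The case against.** The strongest reply is that the table is only an example. Section 11.6 requires the center to weigh the whole event, including device uploads and medical records, and its definitions already send unresolved cases to *Possible*. Its *Not related* criteria also ask whether stopping the device affected the event, which should make a careful investigator consider the route of insulin. That is a fair limit on the harm. It does not make row 1 right: the example states what the rating would be, and a coordinator matching a description to a row will find one that fits.

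A second reply is that the gap is narrow, and this stands in part. Section 6.7 specifies rapid-acting insulin, so a set that is still failing should let glucose rise again once the injection wears off. If the set is then changed, row 2 fits. If control holds on the same set, that is evidence that the set was delivering, and *Not related* is reasonable. The remedy should allow for this.

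A third reply is that other checks exist, and it stands. The Clinical Events Committee reviews severe hyperglycemia reports whatever the investigator's relatedness code, its listed considerations include infusion set issues, and its classification prevails in the analysis (Section 12.1).

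A reader might infer more than the documents support:

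- **That severe hyperglycemia events would be hidden.** They are still recorded with their treatment (Section 11.1). They count in the Data Monitoring Committee's severe hyperglycemia rate and in the SAP's incidence summaries (7.9.6, 7.10) without regard to relatedness.
- **That stopping decisions or study success could change.** Table 5 has no reference value for the device related rate, the expedited steps in Section 12.2 do not list severe hyperglycemia, and SAP 7.9.1 bases pass/fail on the two primary endpoints.
- **That recovery after an injection implicates the set.** It does not; it leaves the question open.

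**Conclusion.** The point holds as a minor one. Row 1 lacks a condition on insulin route, and for a silent set failure treated by syringe or pen and left in place it gives a rating that the general text of 11.6 does not support. The effect is confined to the investigator's relatedness coding and the device related rate seen by the Data Monitoring Committee, and it is open to correction by the Clinical Events Committee.

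How often this would happen cannot be estimated. The documents give neither a rate of silent set failure nor the share of events treated by injection without a set change. The conclusion rests on reading row 1 as it is worded and on the premise that some staff will code from the example rather than work through the definitions.

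**What to change.** In the Section 11.6 example:

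- Replace row 1 with: *Glucose improved, or stayed controlled after any injection wore off, with insulin delivered by the pump through the same infusion set and site, and no pump or set fault: Not related.*
- Add a row: *Glucose improved after insulin by syringe or pen without an infusion set/site change, no later evidence that the same set was delivering, and no other cause established: Possible.*
- Keep rows 2 and 3. Descriptions that match no row fall to the general definitions.

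The cost is one row reworded and one added. No visits, subjects or data items are needed, since treatment and event details are already recorded. The downside is that a few events with unrelated causes, such as illness that was never established as the cause, will be coded *Possible*. That is in line with the default 11.6 already sets for events that cannot be assessed.

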## CIP337 Clinical Investigation Plan Image: Comparison of the second s

#### **11.7 Anticipated or Unanticipated**

If an AE is determined to be related to the study device the sponsor will then assess the event to determine if it is anticipated or unanticipated.

- **Anticipated:** the event is identified in the CIP; labeling; report of priors/ Investigator's Brochure (IB) or user guide.
- **Unanticipated:** the event has not been previously identified in the CIP; labeling; report of priors/IB or user guide.

### **12.** Data Review Committees

#### **12.1 Clinical Events Committee**

A clinical events committee (CEC) consisting of external physicians with an expertise in endocrinology and the management of diabetes including insulin pumps and CGM will be convened. The CEC will review AEs as required per CIP, which include reports of:

- Serious adverse event
- Serious adverse device effect
- Unanticipated adverse device effect
- Severe hypoglycemia
- Diabetic ketoacidosis
- Severe hyperglycemia

During the study, the following steps will be taken for:

- Unanticipated adverse device effects (UADE)
- Device related DKA
- Device related severe hypoglycemia

CEC is to review and adjudicate the event within 10 business days from the time that the sponsor is notified. Adjudication will occur once all applicable documentation has been received and reviewed by the CEC.

The CEC will assess events to determine agreement or disagreement with the investigator classification of an event.

If the CEC disagrees with the investigator's classification of the event, the rationale will be provided to the investigator. If the investigator agrees with the CEC's adjudication, the CRF documenting the AE will be updated accordingly.

If the investigator does not agree with the CEC's adjudication classification, both determinations will be provided within the final report; however, the CEC's adjudication will be used for data analysis. The disagreement will also be included in reporting to IRBs and regulatory authorities, if required.

The CEC may review applicable information for device related AEs which may include:

- Whether or not the event was unanticipated
- Review of sensor data from CareLink Personal/CareLink system software report (when applicable)
- Review of pump data from CareLink Personal/CareLink system software report (when applicable)
- Misuse of the device by the user

Review of events may require the following information. Final disposition may be delayed based on obtaining this information:

- Monitoring by sponsor at investigational center
- Device return and failure analysis
- CareLink Personal/CareLink system software upload and review of software reports
- Subject clarification to investigational center regarding details about the event
- Source documents that support event: Paramedic records; ER records; Lab records; Hospital admission and discharge summary

The following factors should be carefully considered in the CEC's recommendation to sponsor:

- 1. Was the severe hypoglycemia or DKA related to the AHCL algorithm, or was it related to a known insulin pump risk? For example, a question that may be considered in DKA would be whether the event was related to an infusion set issue or caused by the AHCL algorithm.
- 2. Another important consideration would be if the severe hypoglycemia, severe hyperglycemia or DKA event was related to a device malfunction versus patient non-compliance. For example, if a software anomaly leading to an under-delivery of insulin is discovered versus the subject repeatedly ignoring alarms prompting the subject to take action.
- 3. Severe hypoglycemia, severe hyperglycemia or DKA caused directly by an infusion set issue when the study pump is functioning as intended would likely result in acceptance to proceed with the study versus severe hypoglycemia or DKA that are directly caused by the AHCL algorithm or a device malfunction might stop study enrollment or entire study altogether.
- 4. It should be noted that the final determination of causality related to 780G system that is made by the CEC may include additional factors which the members consider to be clinically relevant and important.

D00459337

Page 73 of 97

## **12.2 Data Monitoring Committee**

A data monitoring committee (DMC) consisting of external physicians with an expertise in Endocrinology and the management of insulin-requiring diabetes including CGM, along with an external statistician will be convened to review study progress and safety. The Board will convene approximately every 90 days. The Board will also meet when ad hoc review is required.

## The DMC will perform 3 main functions:

**First:** DMC will track and trend the overall safety of the study. Event rate, defined as number of events per 100 patient years will be reviewed by the DMC with respect to the following:

- Event rate of all SAEs
- Event rate of severe hypoglycemia
- Event rate of severe hyperglycemia
- Event rate of DKA
- Event rate of device related AEs

**Second:** Based on their meetings, DMC will recommend a decision to the sponsor regarding the following:

- Whether or not enrollment should be halted.
- Whether or not the entire study will need to be stopped including for those subjects who have received study devices already.

Note: If it is decided to withdraw subjects from participation in the study or if the study is stopped, subjects will be followed-up in accordance with standard practice by their own providers.

## Third:

During the study, the following steps will be taken for:

- Unanticipated adverse device effects (UADE)
- Device related DKA
- Device related severe hypoglycemia
- 1. Investigational center staff will notify the sponsor within approximately 24 hours of investigator or study coordinator awareness of events described above.
- 2. Sponsor will notify the FDA within approximately 3 business days of awareness of the event and provide updates to the agency as information becomes available.

CIP337 Clinical	IP337 Clinical Investigation Plan		
D00459337	Version A	Page 74 of 97	Medtronic

- 3. DMC is to meet within 10 business days from CEC adjudication of the event. The investigator should be available to answer questions from DMC, as needed.
- 4. Based on their review, DMC will recommend that the sponsor make a decision regarding the following:
  - a) Whether or not subject enrollment may continue.
  - b) Whether or not new subject enrollment should be suspended, with enrolled subjects continuing in the study.
  - c) Whether or not the entire study should be stopped, including those subjects who have already received study devices.
- DMC and/or IRB will recommend whether or not the study should be stopped based on the number of events that have occurred during the study, weighed against the potential benefits of continuing the study.

Note: If it is decided to withdraw subjects from participation in the study or if the study is stopped, subjects will be followed-up in accordance with standard practice by their own providers.

## General guidance for DMC's recommendations to sponsor should be based on the following:

In general, a DMC recommendation regarding study stoppage or resumption of enrollment should be made to the sponsor within 1 week of the DMC meeting where the determination is made. However, if more data is needed, the DMC may meet again to re-assess their decision within 2 weeks or when required data becomes available.

In their recommendation to the sponsor, the DMC may take into account the thresholds listed below for the number of subjects experiencing hypoglycemia requiring assistance from another person or DKA to identify when the number of subjects experiencing these events exceeds the number that would be anticipated for the study population over the duration of this study. These thresholds should be interpreted with caution due to potential differences in study populations and study design.

- a. Rates taken from type 1 exchange (Cengiz et. Al, and Weinstock et. Al), are higher than the clinical studies STAR 3, 530G adult in-home study (CEP266) and 530G Pediatric inhome study (CEP287).
- b. Reasons for lower rates of severe hypoglycemia and DKA in the clinical studies mentioned could be related to several factors including but not limited to the exclusion of those with DKA or severe hypoglycemia, additional attention secondary to mandatory study visits, selection bias of motivated patients willing to perform study procedures and access to free study devices during the course of the study.
- c. The DMC should consider stopping study if rates of severe hypoglycemia and DKA are significantly worse (e.g., higher) in AHCL than rates provided by clinical trials mentioned in **Table 5**.
- d. Age consideration may also be factored in by the DMC. For example, severe hypoglycemia rates in those >25 years may be higher than those 25 years and below.

CIP337 Clinical Investigation Plan			
D00459337	Version A	Page 75 of 97	Medtronic

e. Should DKA and/or severe hypoglycemia occur early in the study, the DMC should consider that the higher event rate may not necessarily represent a significant safety concern.

